9.4 Enrollment

All subjects who sign the ICF will be considered eligible for this study. Subjects who are eligible and meet all the inclusion criteria and do not meet any of the exclusion criteria will be considered enrolled in the study. Enrolled patients who have persistent, stable AF will be randomized and treated according to the research procedures described above.

9.5 Randomization

All enrolled patients who develop persistent, stable AF will be randomized using a simple randomization scheme.

9.6 Assignment of Subject Identification Number

All enrolled subjects will be assigned a three-digit subject identification number in sequential order, starting with 001.

10. DATA COLLECTION

Preoperative, intraoperative, and postoperative data will be recorded and entered in the appropriate data collection sheets for all randomized patients. Study data will not be collected on non-enrolled patients or enrolled patients who are not randomized. Data will include, but is not limited to, previously-obtained preoperative, intraoperative, and postoperative data, concomitant procedures, procedure related complications and adverse events. All study data will be maintained on a REDCap database and will only be accessed for study purposes. A list of the data to be collected is provided below:

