9. RESEARCH PROCEDURES

All enrolled patients will receive the standard of care perioperative institutional protocol for their cardiac surgical procedure. The preoperative and intraoperative management will be performed at the discretion of the cardiovascular surgery team, the anesthesia team, and other healthcare teams. The postoperative management will be performed at the discretion of the cardiovascular surgery team and the consultant anesthesiology critical care team according to standard management protocols.

As part of standard postoperative management, all patients will undergo continuous electrocardiographic (ECG) monitoring in the postoperative period. If new AF is identified within the first 72 hours after they are admitted to ICU following their surgical procedure, the patient will be assessed for hemodynamic stability. If the patient is unstable (SBP <90 mmHg)

or requires a significant increase in vasopressor infusion (an increase of more than 1.5x in baseline infusion rate) to maintain SBP>90 mmHg, the standard of care patient management will be provided and the patient will not be randomized to either study group. If the patient is stable (SBP>90 mmHg and requires less than 1.5x more vasopressor infusion to maintain SBP>90 mmHg), the patient will be given up to 15 mg IV metoprolol, in divided doses, and monitored for 20 minutes for conversion to NSR. If stable AF persists, the patient will be randomized according to the plan described below to either the conventional amiodarone dosing regimen (CDR) or to the repeated amiodarone bolus dosing regimen (RBDR).

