13. POTENTIAL RISKS

Because this study compares 2 amiodarone dosing strategies already used in the proposed study population, there are no specific study-related risks of amiodarone administration. Regardless of whether they are enrolled in this study, patients with persistent, postoperative stable AF will receive amiodarone IV bolus and infusion, unless they have a contraindication to its uses. These patients may receive either the CDR or the RBDR, based entirely on clinician preference. In this study, we are comparing the efficacy and safety of the currently used dosing regimens.

The primary risk of this study is, therefore, only a risk of breach of confidentiality.

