21. DATA AND SAFETY MONITORING

Each subject will be monitored for adverse events (AE) and serious adverse events (SAE) by the PI and/or a member of the research team. Because hypotension and conduction system abnormalities are expected, reversible and treatable complications of amiodarone, they will be monitored but will only be considered AE if they reach "severe" criteria and will only be considered as SAE if they reach "very severe" criteria. Other known complications of amiodarone therapy will be reported as AE or SAE, as appropriate. All AE and SAE will be reported to the IRB per IRB guidelines.

The PI and co-investigators will review the AE and SAE reports after the first 10 patients have completed the research protocol to evaluate patient safety. If, after the first 10 patient have been evaluated, there were no AE or SAE reported, the PI and clinical co-investigators will continue to review the AE/SAE reports after every additional 20 patients have completed the protocol. If, during these periodic reviews, there are reported AE or SAE, the PI and clinical co-investigators will consider whether to continue patient enrollment and study procedures based on an assessment of benefit versus risk. The PI will have the responsibility, in consultation with the

clinical co-investigators, to decide whether to continue the study at each 20-patient interim safety analysis. The PI will inform the IRB if study procedures will be terminated.

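### The protocol gives enrolled patients IV metoprolol before randomisation but bars study data on those not then randomised, which conflicts with its commitment to monitor every subject for adverse events

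*Protocol*

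**What the plan says.** Under Protocol section 9.4 a patient is enrolled once consented and eligible, and randomisation comes later: "Enrolled patients who have persistent, stable AF will be randomized and treated according to the research procedures described above".

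Section 9 describes the step in between. When new AF appears within 72 hours of ICU admission, stability is assessed first. For unstable patients, "the standard of care patient management will be provided and the patient will not be randomized to either study group". For a stable patient, "the patient will be given up to 15 mg IV metoprolol, in divided doses, and monitored for 20 minutes for conversion to NSR". Then: "If stable AF persists, the patient will be randomized according to the plan described below".

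Section 10 sets out data collection for randomised patients and includes "concomitant procedures, procedure related complications and adverse events" among the data. It also contains the bar: "Study data will not be collected on non-enrolled patients or enrolled patients who are not randomized".

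Section 21 has a wider scope: "Each subject will be monitored for adverse events (AE) and serious adverse events (SAE"), with all such events going to the IRB.

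Section 10.3 lists no metoprolol dose or time, even for randomised patients. Its hypotension and bradycardia items refer to the period after amiodarone. The SAP describes comparisons between the two randomised groups only and does not mention the metoprolol step.

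**The concern.** A consented participant can receive a drug named in the research procedures, respond to it well or badly, and leave the trial's data because of that response. Two things are at stake.

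- **Safety accounting.** Section 10 shuts out adverse-event data on the people whom section 21 says are monitored. Staff who follow section 10 and staff who follow section 21 would act differently on the same event.
- **Participant flow.** The trial could not report how many patients with stable AF were removed by conversion and how many by loss of stability. It therefore could not describe the population to which its result applies, or explain a recruitment shortfall.

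A smaller matter concerns randomised patients. Hypotension, bradycardia and heart rate are assessed from the start of amiodarone, soon after a variable dose of a beta-blocker that no listed field captures. Section 11.4 nevertheless plans to model postoperative factors that affect efficacy and safety.

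**Working it through.** No sample size, power or alpha figure is at issue, so the plan has no figure to reproduce. The check is mainly a comparison of sections.

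1. *Is the patient enrolled when metoprolol is given?* Yes. Section 9.4 places enrolment before randomisation, and section 8 allows no study procedure before signed consent.
2. *Who leaves at this step?* Randomisation requires persisting stable AF. A patient who converts does not meet that condition. A patient whose AF is no longer stable does not meet it either, but this is an inference: section 9 assesses stability before metoprolol and describes the 20 minutes as observation for conversion.
3. *What does section 10 do with them?* They are enrolled and not randomised, so its bar applies. Adverse events are among the data it names.
4. *Does section 21 resolve this?* Not clearly. It covers each subject, but it treats hypotension and conduction abnormalities as expected effects of amiodarone that become AEs only at the severe grade. It does not address an event after metoprolol and before amiodarone. Its periodic reviews count patients who have completed the protocol, and it does not say whether a patient stopped at this step counts.
5. *What can still be counted?* Enrolled minus randomised. At the planned numbers (section 5: 150 enrolled; section 11: 60 randomised) that is 150 − 60 = 90. This total mixes patients with no AF, AF outside the 72 hours, unstable AF, and exit after metoprolol, and no field separates them.
6. *Is there an allowance for loss at this step?* Section 5 expects about 60 patients with stable AF, and section 11 analyses after 60 are randomised. The two figures agree only if nobody leaves in between.

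For scale only, let f be the share leaving at the metoprolol step. The documents give no value, so the range below is an assumption. If 60 patients reach the step, 60 × f leave. To randomise 60, the number who must reach it is N = 60 / (1 − f), rounded up, and N − 60 have no study data.

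| f (assumed) | Leave, if 60 reach the step | Randomised | N needed for 60 randomised | N − 60 |
|---|---|---|---|---|
| 5% | 3 | 57 | 64 | 4 |
| 10% | 6 | 54 | 67 | 7 |
| 20% | 12 | 48 | 75 | 15 |
| 30% | 18 | 42 | 86 | 26 |
| 40% | 24 | 36 | 100 | 40 |

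The range is too wide to serve as an estimate. It pools converters with patients who lost stability, so no entry is a count of harms.

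**The case against.** The strongest reply is that these patients do not vanish. Every enrolled subject receives an identification number (section 9.6), a note on eligibility and consent (section 8), and a consent form stored in REDCap (section 14.1). Section 21, read literally, would send a serious event after metoprolol to the IRB. All of this stands. A reader might infer that such patients leave no record at all, or that a harm erases itself; the documents do not support either. What is lost is study data: conversions, blood pressure after metoprolol, reasons for non-randomisation and, if section 10 governs, adverse events.

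A reader might also infer that the primary result is compromised. It is not. The step precedes allocation and is the same for both groups, so it does not bias the comparison of conversion rates or systematically confound the comparison of hypotension or bradycardia.

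The bar can also be defended as data minimisation, given section 13: "The primary risk of this study is, therefore, only a risk of breach of confidentiality". That explains a preference for holding little on non-randomised patients. However, the reasoning in section 13 concerns amiodarone only and does not mention metoprolol, and it does not remove the conflict with section 21.

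Finally, the section 10 list is expressly open-ended, so a metoprolol field is permitted for randomised patients. Being permitted does not ensure that it is collected.

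**Conclusion.** The point holds as a conflict between Protocol sections 10 and 21, with a real but bounded consequence. The bar in section 10 is a stated rule, not a missing detail. Followed as written, it leaves no study data on enrolled patients who convert after the protocol-ordered metoprolol. It may leave adverse events after that drug uncaptured, and it prevents the flow from stable AF to randomisation from being reported by reason.

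The conclusion for converters rests on the text alone. For patients who become unstable it rests on reading the persistence condition as excluding them, which is the natural reading but is not spelled out. The number affected cannot be stated from the documents. The effect is on safety accounting, participant flow and applicability, not on the validity of the randomised comparison. It should be corrected, because the remedy is cheap and touches no treatment.

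**What to change.** Reconcile sections 10 and 21 by amending section 10. For every enrolled patient given the pre-randomisation metoprolol, record:

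- dose given;
- time given;
- rhythm at the end of the 20 minutes;
- lowest SBP by the end of the 20 minutes;
- reason not randomised, where that applies;
- any AE or SAE.

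Section 21 should then say how an event after metoprolol and before amiodarone is classified, and whether patients who stop at this step count towards its periodic reviews. Add metoprolol dose and time to the section 10.3 list for randomised patients.

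The cost is a protocol amendment and about six fields from routine monitoring, for an unknown number of extra patients who have already consented. For randomised patients it is two fields each: 2 × 60 = 120 to 2 × 80 = 160 entries, depending on whether the 20-patient extension is used. Slightly more data would be held on non-randomised patients, which section 14.1's confidentiality arrangements already cover.

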10.1 Preoperative data

- Demographics (sex, age, height, weight, and body mass index)
- Preoperative use of beta-blocker therapy
- Preoperative left ventricular ejection fraction
- Preoperative tobacco use (smoking)
- Preoperative alcohol use
- Preoperative benzodiazepine use

10.2 Intraoperative data

- Surgical procedure(s) performed
- Date/time of OR entry
- Date/time of anesthesia induction
- Date/time of surgery start
- Date/time of cardiopulmonary bypass start
- Date/time of aortic cross-clamp
- Date/time of aortic cross-clamp removal
- Date/time of cardiopulmonary bypass end
- Estimated blood loss
- IV fluid administered
- Blood transfused

10.3 Postoperative data

- Date/time of ICU admission
- Date/time of extubation

- Date/time of ICU discharge
- Date/time of hospital discharge
- Vasopressor (norepinephrine, vasopressin) use at ICU admission
- Inotrope (dopamine, epinephrine, milrinone, dobutamine) use at ICU admission
- Pacemaker use at ICU admission
- Date/time of first AF
- Presence of rapid ventricular response with first AF
- Heart rate at time of AF diagnosis
- Heart rate at initiation of study group treatment (initial amiodarone bolus)
- Hourly heart rate for 24 hours, beginning at start of study group treatment
- Date/time of study randomization
- Date/time of first study drug administration
- Total number of amiodarone boluses administered
- Restoration of normal sinus rhythm by ICU discharge
- Restoration of normal sinus rhythm by hospital discharge
- Date/time of normal sinus rhythm
- Total number of stable AF episodes (excluding initial episode) prior to ICU discharge
- Total number of stable AF episodes (excluding initial episode) prior to hospital discharge
- Presence of hypotension (SBP < 90 mmHg or increase in vasopressor infusion by 1.5x to achieve SBP > 90 mmHg) after amiodarone therapy during amiodarone IV load period
- Severity of hypotension after amiodarone therapy during amiodarone IV load period
 - Mild: No intervention needed
 - Moderate: Hypotension resolved after fluid bolus

- Severe: Hypotension requiring vasopressor or inotropic therapy
- Very Severe: Hypotension requiring multiple vasopressor or inotropic therapies
- Presence of bradycardia (HR <60 beats per minute) after amiodarone therapy during amiodarone IV load period
- Presence of conduction abnormality during amiodarone IV load period
- Severity of conduction abnormality during amiodarone IV load period
 - Mild: No intervention
 - Moderate: Temporary pacemaker required for ≤ 12 hrs
 - Severe: Temporary pacemaker required for 12-48 hrs
 - Very Severe: Temporary pacemaker required for ≥ 48 hrs or permanent pacemaker required
- Presence of pulmonary fibrosis related to amiodarone therapy
- Severity of pulmonary fibrosis related to amiodarone therapy
 - Mild: No intervention needed
 - Moderate: Discharged on oxygen at night only
 - Severe: Discharged on continuous oxygen
 - Very Severe: Discharged on mechanical ventilation or patient death due to pulmonary fibrosis

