11.2 Primary Objective

To assess the primary objective, the number and percentage of patients in each group who have converted to NSR after 24 hours will be calculated. The number of patients who convert to NSR in each group will be compared with either the Fischer's Exact test or the Chi-Square test, as appropriate.

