- To compare the incidence and severity of conduction abnormalities, the number of patients who develop bradycardia will first be calculated and reported as number and percentage. The number of patients with bradycardia will be compared with the Fischer's Exact test or the Chi-Square test, as appropriate. The number of patients who develop mild, moderate, severe or very severe conduction abnormalities will then be calculated and reported as number and percentage. The number of patients with each severity class will then be compared between groups using Somers' D test for ordinal data.

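### Conduction-abnormality incidence is compared only as HR <60 with no rule for paced rates, and the severity grade does not separate pacing that preceded the study drug from new pacing.

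*Protocol*

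**What the plan says.** Protocol Section 3.2 sets a secondary objective on the incidence and severity of conduction abnormalities. Section 10.3 lists these items:

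- For heart rate: "Presence of bradycardia (HR <60 beats per minute) after amiodarone therapy during amiodarone IV load period"
- As a separate item for conduction: "Presence of conduction abnormality during amiodarone IV load period"
- Grades for that second item: mild (no intervention), then "Moderate: Temporary pacemaker required for ≤ 12 hrs", followed by "Severe: Temporary pacemaker required for 12-48 hrs" and lastly "Very Severe: Temporary pacemaker required for ≥ 48 hrs or permanent pacemaker required"
- At baseline, "Pacemaker use at ICU admission"

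Section 11.3, repeated in SAP Section 1.3, handles incidence through bradycardia: "The number of patients with bradycardia will be compared with the Fischer's Exact test or the Chi-Square test, as appropriate". Severity classes are then compared with Somers' D. The presence-of-conduction-abnormality item is collected, but no incidence comparison is planned for it.

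Section 21 treats a conduction abnormality as an AE only when it is graded severe and as an SAE only when it is graded very severe. Section 9 allows AF to be identified at any time in the first 72 hours after ICU admission.

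For the primary endpoint, Section 11.2 says "the number and percentage of patients in each group who have converted to NSR after 24 hours will be calculated". NSR is not defined there, in Section 3.1 or in SAP Section 1.2, and no passage classifies a paced rhythm.

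**The concern.** The plan expects some patients to be paced, since it records pacemaker use and grades conduction events by hours of pacing. The two halves of the conduction objective nevertheless use different events. Incidence is a heart-rate threshold that pacing can hide, while severity is a count of pacing hours. The same patient can score high on one and zero on the other.

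The severity item also lacks a condition tying it to the study drug. That grade feeds AE and SAE reporting, and the periodic safety reviews in Section 21 rest on those reports. Pacing present for surgical reasons could enter as a drug complication, and a pacing need that arose on the drug could be missing from the incidence table. Section 21 itself calls conduction abnormalities an expected complication of amiodarone, and the arms differ in amiodarone dose, so the classification should be unambiguous.

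**Working it through.** **No plan figure to reproduce.** The documents give no pacing frequency, pacing rate, bradycardia rate or power figure. The first two steps are textual; the last two are illustrations on assumed rates.

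**Step 1: incidence against severity.** Consider a patient with a conduction abnormality during the load whose pacing captures at 60 or above throughout.

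| Item (Section 10.3) | Result |
|---|---|
| Bradycardia, HR <60 | No, if the paced rate is what is recorded |
| Conduction abnormality present | Yes, but no incidence test is planned |
| Severity grade | Moderate, severe or very severe, by hours |

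The patient appears in the Somers' D comparison and not in the incidence comparison.

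**Step 2: the pacing clock.** The IV load lasts 6 + 18 = 24 hours after the initial bolus (Section 9). The top grade needs 48 hours of temporary pacing or a permanent pacemaker, so pacing hours outside the load must count. The text does not say whether these are later hours, earlier hours or both. Suppose pacing has run since ICU admission and AF begins at hour T, with T at most 72. About T hours have then accrued at the first bolus. If the clock starts with pacing, T above 12 already meets the severe grade (AE) and T of 48 or more meets the very severe grade (SAE), before any study drug has acted. Bradycardia and hypotension are both restricted to events after amiodarone therapy; the conduction items are not.

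**Step 3: illustration for bradycardia.** Assumed true rates are 20% CDR and 40% RBDR, with n = 30 per arm (Section 11), two-sided 0.05, and a share m of events masked equally in both arms. With p̄ the mean of the two rates:

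power = Φ{ [|p₂ − p₁| − 1.96·√(2p̄(1 − p̄)/n)] / √([p₁(1 − p₁) + p₂(1 − p₂)]/n) }

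| m | Observed rates | Power |
|---|---|---|
| 0 | 20% v 40% | 39% |
| 0.25 | 15% v 30% | 28% |
| 0.50 | 10% v 20% | 19% |

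For m = 0.50: (0.10 − 1.96 × 0.0922)/0.0913 = −0.88, and Φ(−0.88) = 0.19.

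Unequal masking can move the difference either way. If half is masked in RBDR only, 20% v 40% becomes 20% v 20%. If half is masked in CDR only, it becomes 10% v 40%.

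**Step 4: sensitivity of the primary count to paced patients.** Assume AF has ended by 24 hours in 26/30 RBDR and 18/30 CDR patients. P-values are uncorrected chi-square, with Fisher's exact in brackets.

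| Paced patients scored as not converted (RBDR, CDR) | Count | p |
|---|---|---|
| 0, 0 | 26 v 18 | 0.020 (0.039) |
| 1, 1 | 25 v 17 | 0.024 (0.047) |
| 3, 1 | 23 v 17 | 0.100 (0.170) |

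The result depends on the assumed split. At one patient per arm the p<0.05 conclusion does not change; at three to one it does.

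**The case against.** Several stronger readings are tempting, and the documents do not support them.

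- **That pacing is ignored.** It is not. Pacing hours define the upper three severity grades, those grades are compared between arms, and they set AE and SAE status. A patient who becomes pacing-dependent on the drug is captured there.
- **That a paced patient cannot register bradycardia.** Monitoring is continuous (Section 9) and any HR <60 after amiodarone counts. A fall below 60 before pacing starts, or during a pause, would still be recorded. Masking needs pacing that already captures at 60 or above, and the documents give no pacing rate.
- **That a patient paced at 24 hours is a primary-endpoint failure.** No passage says so. NSR is undefined, and the wording about having converted could credit NSR reached before pacing. The classification is unspecified.
- **That this is bias tied to treatment.** Pacing carried over from before the first bolus predates the effect of the assigned regimen and should balance between arms in expectation. Whether new pacing differs by arm is unknown.

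Two further defences have some force. The grades refer to pacing that is required, for a conduction abnormality present during the load, so incidental pacing is not automatically graded. The data list in Section 10 is also expressly not exhaustive, and grading by hours implies that some duration is read from the chart. Neither supplies a new-onset condition, a clock start or a rule for paced rates. The mismatch between the incidence and severity definitions therefore stands.

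**Conclusion.** The point holds as a definitional defect in a secondary safety endpoint. The incidence comparison can miss patients whom the severity scale grades moderate to very severe. The severity scale can also grade, and send to AE or SAE reporting, pacing that began before the first study bolus. Both follow from the text of Sections 10.3, 11.3 and 21 and need no assumed rate.

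The size and direction of any effect on the comparison between arms cannot be determined, because the frequency of pacing is not given. The 39% to 19% range in power rests on assumed bradycardia rates and equal masking. The primary-endpoint counts rest on an assumed split of paced patients and show only that a few classification decisions may matter at 30 per arm. They are grounds for a sensitivity analysis, not evidence that the primary result is biased.

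**What to change.** In Protocol Section 10.3, record pacing status at the first study bolus and at 24 hours, with pacing start and stop times during the IV load.

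In Section 11.3 and SAP Section 1.3, define the incidence event as HR <60, or pacing newly started or newly required after the first study bolus. Add the post-amiodarone condition to the conduction presence and severity items. Grade severity only on new pacing, with hours counted from the first study bolus.

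Keep NSR as the primary endpoint. In Section 11.2 and SAP Section 1.2, add a sensitivity analysis that classifies patients who are paced and without AF at 24 hours as converted. Replacing NSR with absence of AF as the primary would change the question the trial asks, and this problem does not require it.

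The cost is a few chart items and some endpoint wording, with no new procedure. In a few continuously paced patients the underlying rhythm may be unreadable, so a default classification must be stated before the data are examined.
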